7.4. On study and pre-study closure activities

7.4.1. Data monitoring

The Data Monitoring Committee (DMC) consists of the Principal Investigators (or their representatives), the Medical Monitor, and Sponsor representatives. It may also include invited experts (such as a PK or PD data expert). During Part 1 the DMC will meet by telephone (or in person if possible) to review safety data from the first treatment cycle of the current cohort under evaluation. The DMC will also convene

periodically during Part 2, after every 2 months or a further 6 patients have been enrolled (whichever comes first), to consider ongoing safety and tolerability at the RD. They will also consider PK and PD data as available and ongoing safety data from prior cohorts. Appropriate representatives of the Sponsor and the coordinating personnel will also attend and minute the meeting. Decisions of the DMC will be documented, filed in the eTMF, and will be distributed to all study sites.

Further details on the composition of the DMC, as well as the process for data review and decision-making, are described in the DMC charter for this study.

The DMC will:

- review the safety data from the first cycle of treatment for each cohort during Part 1 and make dose-escalation decisions;
- consider other AEs, or possible trends in AEs, during Part 1 which may inform dose escalation decisions or selection of the RD for Part 2;
- confirm the MTD or MAD and select the RD for further evaluation in Part 2;
- review the safety data package for Part 1; perform ongoing assessment of safety, antileukemic activity, PK and PD data in Part 2;
- support the implementation of supportive care guidelines during the study, by ongoing review of AEs and need for treatment delays; consider these data both for DLT evaluation, possible need for dose modification for individual patients, or recommendation for withdrawal (see Section 3.4 of the study protocol).

7.4.2. Protocol Deviations and Data Review Meeting

Categories of protocol violations will be defined and will be integrated in the statistical analysis.

During the Data Review Meeting that will take place at the end of the study, the final list of Protocol Deviations will be defined. (Please refer to MedPace Protocol Deviation Plan V3.0 of 04 November 2021 for the full deviation categories list).

8. Determination of sample size

Due to the nature of the study, no formal sample size calculation is applicable. However, under Protocol Version 12.0, approximately 65 evaluable patients with AML were planned to be enrolled in this study, with 20 of them to be enrolled in the all-comers cohort and 20 in the IDH-mutants cohort (Part 2).

The study Part 1 was initially designed with an accelerated titration design for the first 4 cohorts, then a 3+3 design had to be followed from the former fifth cohort (150 mg dose level) onwards.

However, following the occurrence of 2 DLTs at the 150 mg dose level, one of which resulted in a fatal treatment-related outcome, the study design was revised to follow a 3+3 design from Cohort 2 onwards in order to assess for DLT, adverse events, and adequate PK profile data from at least 3 patients in each dose level from 50 mg onwards.

The final number of patients treated in Part 1 was 25 and 125 mg was considered the RP2D.

This cohort was then expanded to enroll 20 additional patients. Nevertheless, 3 patients were replaced and a total number of 23 patients were treated in this study phase. The replacement occurred when patients were not considered evaluable for safety and/or lacked one post-treatment bone marrow disease assessment.

9. Randomization Methodology

The study is non randomized.

10. Stopping Rules and Blinding

10.1. Stopping Rules

A data monitoring committee (DMC) external to both the Sponsor and clinical research organization (CRO) will be responsible for ongoing monitoring of the safety and efficacy according to the DMC Charter. The DMC will meet on a regular basis and will make recommendations as to whether the trial should continue, be amended, or be discontinued based on ongoing reviews of safety and efficacy data. DMC responsibilities and review schedules are outlined in an DMC charter.

10.2. Blinding

This is an open-label study; thus, study subjects and investigators will not be blinded to treatment assignment.

11. Statistical analysis and methods

11.1. Multiplicity adjustment

This section is Not Applicable

11.2. Descriptive statistics

All study variables will be presented by cohort, dose and overall, by using the appropriate descriptive statistics according to the variable nature, unless otherwise specified:

- **Continuous variables:** number of non-missing observations, arithmetic mean, median, standard deviation (SD), minimum, maximum;
- **Categorical variables:** number of non-missing observations and column percentages (N, %);
- **Time to event variables:** number of non-missing observations, number and percentage of censored observations, 1st quartile, median and its 95% Confidence Interval (CI), 3rd quartile, Kaplan-Meier survival curves.

The behaviour over time of study variables will be summarised by cohort and overall as follows:

- **Continuous variables:** descriptive statistics for each time point of interest;
- **Discrete variables:** descriptive statistics for each time point of interest.

11.3. Data imputation

The missing values will not be imputed because, for all the analyses, an observed-cases approach will be applied.

Regarding time-to-event variables analysis:

- OS, if a subject is censored with respect to the event of interest the censoring date is defined as the date of the last performed visit;
- RFS, EFS and DoR, if a subject is censored with respect to the event of interest the censoring date is defined as the date of the last relapse/progression/event-free disease assessment.

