5.4.2. Secondary endpoints

Study Part 1:

- The number and frequency of AEs, safety laboratory, vital signs and ECG assessments

Study Part 1 and 2:

- Disease assessment will involve evaluation of leukemic blast proportion in the bone marrow. Hematologic parameters from the routine local assessments including blast percentage (where applicable), platelet count, and other relevant parameters such as transfusion dependence will also contribute to this assessment. Disease assessment will also include an aliquot of bone marrow aspirate/biopsy that will be centrally stored for future analysis (e.g. minimal residual disease), if any.
- Overall response rate (ORR), defined as the proportion of patients who have a complete remission (CR), complete remission with incomplete hematologic recovery (CRI), complete remission with partial hematologic recovery (CRh) or morphologic leukemia-free state (MLFS) response to therapy.
- Partial remission (PR) rate, defined as the proportion of patients who have a partial remission response to therapy.
- Duration of response (DoR), defined as the time from the date of first CR, CRI, CRh, CRMRD-, MLFS or PR until the date of documented relapse of any type, progressive disease or death due to disease progression for subjects who achieve CR, CRI, CRh, CRMRD-, MLFS or PR. Subjects who either do not relapse or die without report of relapse are considered nonevents and censored at their last relapse-free disease assessment date. Subjects who undergo an allogeneic HSCT will be considered non events and censored at the time of HSCT

- Relapse free survival (RFS), defined as the time from the date of first CR, CRi, CRh or CRM RD- until the date of documented relapse or death from any cause. Subjects who either do not relapse or do not die are censored at their last relapse-free disease assessment date.
- Event free survival (EFS), defined as the time from the date of first study drug intake until the date of documented relapse, treatment failure or death from any cause. For a subject who did not experience the event, EFS is censored at the date of last relapse-free disease assessment. Subject is not censored at HSCT.
- Overall survival (OS), defined as the number of days between the first study drug administration and death from any cause. Patients without the event are censored at the last date of follow-up.

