7.3. Analysis populations

The following analysis populations will be considered in the statistical analysis:

- **Safety population:** the safety set consists of all patients that have received at least one dose of SEL24/MEN1703.
- **DD population:** the dose determining set will consist of all patients in each cohort that have completed one cycle of treatment and patients that discontinued earlier due to a DLT occurring in this period. This population will be used for the dose escalation Part 1.
- **PK population:** all patients who received any dose of SEL24/MEN1703 and have sufficient data for PK analysis. Therefore, all subjects receiving study drug and having at least 1 measurable drug concentration will be included in the PK population. If there are subjects who do not have sufficient samples for the PK non-compartmental analysis (NCA), a modified NCA will be conducted in which some or all PK parameters may not be estimated for those subjects, but available PK concentrations will still be tabulated and graphed.

For some objectives (e.g. anti-leukemic or PD activity), a subgroup of patients of the safety set with respective baseline and post-baseline measurements will be used along with the safety population.

- **Efficacy population:** the efficacy set will consist of all patients in each cohort that have completed one cycle of treatment (considering both the treatment and the washout period - 21 days) and have taken at least 75% of the study drug during the first cycle.

Thus, anti-leukemic activity will be analyzed on both the safety and the efficacy population.

Patients who were screened but did not receive any treatment will be listed and will not be part of any summary table.

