12.1. Efficacy analysis

The Overall Survival (OS) is calculated as:

- In case of all-cause death:
 $OS = date\ of\ death - date\ of\ first\ study\ drug\ administration + 1;$
- In case of censored information not for drop-out:
 $OS = date\ of\ end\ of\ observation\ period\ (i.e.\ study\ end / end\ of\ survival\ follow-up) - date\ of\ first\ study\ drug\ administration + 1;$
- In case of censored information for drop-out:
 $OS = last\ date\ known\ alive - date\ of\ first\ study\ drug\ administration + 1.$

The Relapse Free Survival (RFS) is calculated as:

- In case of relapse or all-cause death:
 $RFS = date\ of\ relapse\ or\ death\ (whichever\ comes\ first) - date\ of\ first\ CR,\ CRi,\ CRh\ or\ CR_{MRD-} + 1;$
- In case of censored information:
 $RFS = date\ of\ last\ relapse-free\ disease\ assessment - date\ of\ first\ CR,\ CRi,\ CRh\ or\ CR_{MRD-} + 1.$

The Event Free Survival (EFS) is calculated as:

- In case of relapse, treatment failure or all-cause death:
 $EFS = date\ of\ relapse,\ disease\ progression,\ treatment\ failure\ (failure\ to\ achieve\ CR/CRh/CRi/CR_{MRD-}\ after\ at\ least\ five\ cycles\ of\ treatment)\ or\ death\ (whichever\ comes\ first) - date\ of\ first\ study\ drug\ administration + 1;$
- In case of censored information:
 $EFS = date\ of\ last\ relapse-free/treatment-failure-free/progression-free\ disease\ assessment - date\ of\ first\ study\ drug\ administration + 1.$

The Duration of Response (DoR) is calculated as:

- In case of relapse, progressive disease or death due to progressive disease:
 $DoR = date\ of\ relapse\ of\ any\ type/progressive\ disease/death\ due\ to\ progressive\ disease - date\ of\ first\ CR,\ CRi,\ CRh,\ CR_{MRD-},\ MLFS\ or\ PR + 1;$
- In case of censored information:
 $DoR = date\ of\ last\ relapse-free\ disease\ assessment - date\ of\ first\ CR,\ CRi,\ CRh,\ CR_{MRD-},\ MLFS\ or\ PR + 1.$

No formal statistical analysis will be performed on anti-leukemic parameters.

Anti-leukemic activity data will be collected throughout Part 1 and Part 2 and will be summarized by cohort, by dose and overall.

Measures of anti-leukemic activity will be computed on both safety and efficacy populations and they will include:

- Changes (absolute and %) in pre- and post-treatment levels of leukemic blasts in the peripheral blood and/or bone marrow;
- Number and percentages of patients who reported as best overall response one of the following: CRM RD-, CR, CRh, CRi, MLFS, PR, SD, PD;
- Duration of response (DoR);

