Efficacy Tables (to be performed on both efficacy population as well as safety population)

Table 3.1: Summary of Tumor Response by Visit
 Table 3.2: Summary of Tumor Response Endpoints
 Table 3.3: Summary of Time to Event Endpoints

PK Tables

Table 4.1: Summary statistics of MEN1703 PK concentration in plasma by cohort, cycle, day, IDH mutational status and nominal time point, and by dose, cycle, day, IDH mutational status and nominal time point
 Table 4.2: Summary statistics of MEN1703 PK parameters by cohort, cycle, day, IDH mutational status and nominal time point, and by dose, cycle, day, IDH mutational status and nominal time point.
 Table 4.3: Summary statistics of MEN1703 PK concentration in urine by cohort, cycle, day, IDH mutational status and nominal time point, and by dose, cycle, day, IDH mutational status and nominal time point
 Table 4.4: Summary statistics of MEN1703 urinary PK parameters by cohort, cycle, day, IDH mutational status and nominal time point, and by dose, cycle, day, IDH mutational status and nominal time point
 Table 4.5: Summary statistics of MET3 PK concentration in plasma by cohort, cycle, day, IDH mutational status and nominal time point, and by dose, cycle, day, IDH mutational status and nominal time point
 Table 4.6: Summary statistics of MET3 PK parameters by cohort, cycle, day, IDH mutational status and nominal time point, and by dose, cycle, day, IDH mutational status and nominal time point.

Table 4.7: Summary statistics of MET3 PK concentration in urine by cohort, cycle, day, IDH mutational status and nominal time point, and by dose, cycle, day, IDH mutational status and nominal time point

Table 4.8: Summary statistics of MET3 urinary PK parameters by cohort, cycle, day, IDH mutational status and nominal time point, and by dose, cycle, day, IDH mutational status and nominal time point

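### The SAP leaves open whether ORR and PR rate count unassessed patients, and overall survival in its efficacy set excludes every death before the end of Cycle 1

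*SAP*

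**What the plan says.** **Response.** SAP 5.4.2 defines ORR and PR rate only as proportions of patients with the given response and names no denominator. On sets, SAP 12.1 says: "Measures of anti-leukemic activity will be computed on both safety and efficacy populations and they will include". The heading of the efficacy tables in SAP 13.2.1 repeats this: "to be performed on both efficacy population as well as safety population".

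Four other statements bear on who is counted within a set:

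- SAP 11.3: "The missing values will not be imputed because, for all the analyses, an observed-cases approach will be applied".
- SAP 11.2 presents categorical variables as non-missing counts with column percentages and does not say what the percentages are taken over.
- SAP 12.1 tabulates "Number and percentages of patients who reported as best overall response one of the following", followed by eight categories from MRD-negative CR to PD. None covers a patient who was not assessed.
- SAP 7.3 says that for anti-leukemic activity, among others, "a subgroup of patients of the safety set with respective baseline and post-baseline measurements will be used along with the safety population".

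**Survival.** SAP 7.3 limits the efficacy set to patients who completed the first cycle, counted as 21 days including washout, and took at least 75% of its drug. SAP 5.4.2 has OS "defined as the number of days between the first study drug administration and death from any cause", and the formula in SAP 12.1 uses the same origin. EFS also starts at first dose. No landmark is given.

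**The concern.** Naming the safety and efficacy sets does not settle how a member without a post-baseline response assessment is counted. Two analysts could follow this SAP and report different ORRs from the same data. An assessed-only rate leaves out patients who died or stopped before a marrow, so it tends to be higher.

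Such patients are to be expected. Unless blood results suggest a response earlier, the first on-treatment marrow is due at Cycle 3 Day 1 (footnote 7 of the assessment schedule), which is day 2 × 21 + 1 = 43 on schedule. The efficacy set requires only Cycle 1, so its members can lack a marrow too.

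The survival problem is separate. Membership of the efficacy set depends on surviving a period that OS then counts as follow-up. Efficacy-set OS is longer by construction and will be shown beside the safety-set figure.

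**Working it through.** **Planned numbers.** SAP Table 1 gives Part 1 as 2+3+3+3+3+7+3+1 = 25. Then 25 + 20 + 20 = 65, the planned total in SAP section 8. All-comers: 20 planned + 3 replaced = 23 treated. Both figures reproduce. The plan states no target response rate, alpha or power.

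**Denominator, all-comers.** With n treated, u unassessed and r responders, the rate is r/n over the whole set and r/(n − u) over assessed patients. Their ratio is n/(n − u). Input: n = 23. Assumptions: r = 4 and the values of u. Intervals are Clopper-Pearson 95%.

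| u | Denominator | Factor | Rate with 4 responders (95% CI) |
|---|---|---|---|
| 0 | 23 | 1.00 | 17.4% (5.0–38.8) |
| 1 | 22 | 1.05 | 18.2% (5.2–40.3) |
| 2 | 21 | 1.10 | 19.0% (5.4–41.9) |
| 3 | 20 | 1.15 | 20.0% (5.7–43.7) |
| 5 | 18 | 1.28 | 22.2% (6.4–47.6) |

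The row u = 3 takes all three replaced patients as unassessed. SAP section 8 gives their reason as not being evaluable for safety, lacking a post-treatment marrow, or both. All 23 were treated, and protocol 3.3 and 7.1 make anyone who took one dose evaluable for safety, so a missing marrow is the likely reason. The replacement text in force when that cohort enrolled is not visible.

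The row u = 5 is there because three is not a ceiling. Protocol 3.3 makes replacement optional and does not allow it for a patient without a marrow whose blood shows clear progression. In the other direction, protocol Appendix D allows PD to be called on peripheral blasts, so a missing marrow does not always mean a missing response category.

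**Denominator, IDH cohort.** About 20 are planned and the number unassessed is not given. With 4 responders, an assumed u = 0, 2, 4, 6 gives 4/20 = 20.0%, 4/18 = 22.2%, 4/16 = 25.0%, 4/14 = 28.6%.

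**OS in the efficacy set.** If survival is exponential with median m, patients known to be alive at day 21 have median m + 21 days. In months, 21/30.44 = 0.69. Protocol 1.1 quotes medians of 2.5 and 6.9 months for other AML populations:

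- m = 2.5: 2.5 + 0.69 = 3.19 months (+28%). Death by day 21: 1 − 2^(−0.69/2.5) = 17.4% of patients.
- m = 6.9: 6.9 + 0.69 = 7.59 months (+10%). Death by day 21: 1 − 2^(−0.69/6.9) = 6.7%.

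**EFS in the efficacy set.** Only deaths are screened out by surviving Cycle 1. Protocol 3.4 lets a patient stay on drug after progression, so a patient can progress in Cycle 1, complete it and still count as an event. Safety-set OS and EFS shift by zero on this account.

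**The case against.** The case for leaving the text alone is reasonable. A patient who was never assessed does not have a response, so a proportion of patients in the set already counts that patient as a non-responder. The observed-cases sentence stands under a heading on imputation and need not redefine the sets. The measured subgroup is to be used alongside the safety population, and SAP 7.3 then concludes that activity is analysed on the safety and efficacy sets. Everything here is secondary and descriptive, and a shift of 20.0 − 17.4 = 2.6 points is small against intervals more than 30 points wide.

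Much of this stands. The all-in-set reading is fair, so a reader who infers that the SAP prescribes an assessed-only rate goes beyond the text. But the observed-cases rule is stated for all analyses, and protocol 8.4 leaves missing values and withdrawn patients to the SAP. Protocol 8.9 also foresees an exact interval for Part 2 response, which needs a fixed denominator.

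A reader might also infer that no leading population exists. Protocol 8.2 largely answers that: the safety set is its default, and SAP 3.1 says the analyses are as the protocol specifies. None of this removes the guaranteed survival time in efficacy-set OS.

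**Conclusion.** The concern holds in two limited parts. First, the ORR and PR-rate denominator is ambiguous; it is not fixed wrongly. The factor of 1.15 assumes that all three replaced all-comers are unassessed and that nobody else is. It should not be read as a maximum. Second, efficacy-set OS excludes every death before the end of Cycle 1. That follows from the definitions; its size (+21 days on the median) rests on an exponential model and on medians from other populations.

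Two stronger readings are not supported:

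- *Safety-set OS is unbiased.* It is free of the 21-day problem, and no more than that is shown. Protocol 3.6 ties survival follow-up to patients evaluable for efficacy, while protocol 5.1 and footnote 18 of the schedule do not. SAP 11.3 censors OS at the last visit performed, but SAP 12.1 uses the end of observation or the last date known alive.
- *Efficacy-set EFS has the same defect as OS.* It is protected from early death only; early progression still counts.

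The effect is on how the reported estimates read. No test or error rate depends on it.

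**What to change.** In SAP 11.3 and 12.1:

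1. Define ORR and PR rate as responders divided by all patients in the named set. Patients without a post-baseline response assessment count as non-responders and appear in a row labelled 'Not evaluable / died before assessment' beside the best-response categories.
2. Report OS and EFS from first dose on the safety set, the protocol 8.2 default, as the main result.
3. If OS is also shown on the efficacy set, start it at a day-22 landmark and label it supportive. Do not landmark EFS, because that would drop the early progressions.

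The cost is SAP wording, one table row, a little extra table work and a slightly lower ORR than an assessed-only rate would give. No new data are needed.

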- 14 SEL24/MEN1703 will be given once daily on D1-14 over 21-day treatment cycles. Doses shall be taken on an empty stomach (at least 2 hours after and 1 hour before eating).
- 15 Blood samples for plasma PK analysis will be taken at C1 D1 pre-dose, 0.5, 1, 2, 4, 6, 8, 10-14 and 24 h (C1 D2 pre-dose), C1 D7 at 4 and 8 h post dose, C1 D14 (or last day of dosing in cycle) pre-dose, 0.5, 1, 2, 4, 6, 8, 10-14 and 24 h (C1 D15), 72 h (C1 D17), 120 h (C1 D19), C2 D1 pre-dose (-1 d tolerance), D7 and 14 (or last day of dosing in cycle) at 2-6 h post dose, C3 onwards D1 pre-dose (-1 d tolerance) and D14 (or last day of dosing in each cycle) at 2-6 h post dose (-2 d tolerance). All sample times are approximate, and every effort should be made to take the samples as close to the specified time given and, where relevant, contemporaneously with blood sampling for PD biomarker assessments. For the C1 D1, D2, D7 and D14 a  $\pm$  5 min window is allowed, for the C1 last day of dosing 24 h (C1D15), 72 h (C1D17) and 120 h (C1D19) samples, a  $\pm$  2 h window is allowed. Please refer to the Lab Manual for full details on sample collection, time-points, processing, storage and shipment.
- 16 Part 1 only. Urine collection for PK analysis will be collected from the first dose of SEL24/MEN1703 until immediately prior to the second dose. Please refer to the Lab Manual for full details on sample collection, time-points, processing, storage and shipment.
- 17 Final study assessments to be conducted up to 30 d (+/- 2 d) from last dose of SEL24/MEN1703. Adverse events and concomitant medications must be assessed to 30 d from last dose of SEL24/MEN1703. Other assessments may be carried out between 7-30 d from last dose.
- 18 An assessment of each patient's disease status and AML-related medications administered will be made approximately every 3 months from last dose of SEL24/MEN1703 for up to 1 year (or until End of Study, whichever occurs first) regardless of the initiation of additional treatments to determine date of progression (where appropriate) and survival status.

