### **3.6. Procedures for Patient Discontinuation**

If a patient withdraws from the study prior to study completion, the reason for withdrawal should be sought and recorded in the patient file and the electronic Case Report Form (eCRF). Every effort will be made to complete the Final Study Visit.

The Final Study Visit will be performed up to 30 days after the last dose of SEL24/MEN1703. Unscheduled assessments showing disease progression and leading to subject's withdrawal can replace the Final Study Visit provided that all assessment/procedures scheduled for this visit are completed.

After the Final Study Visit, all subjects evaluable for efficacy will be followed for survival/disease status according to local practice (a visit or a telephone call) every 3 months from last dose of

SEL24/MEN1703 for up to 1 year (or until End of Study, whichever occurs first), regardless of the initiation of additional treatments.

In the case of a temporary or permanent clinical hold, procedures will be put in place to communicate this to patients and advice provided to sites on how to complete patient eCRFs.

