### 5.1. Schedule of Study Assessments

Each section below provides a summary of study assessments described by visit.

Please also refer to the Schedule of Study Assessments (Table 5) and associated footnotes.

Informed Consent must be obtained using the current version of the PIS/ICF prior to commencing Screening. On dosing days, assessments should be performed prior to SEL24/MEN1703 dosing unless specified otherwise. Additional assessments may be conducted as clinically indicated. Where possible, patients will be followed up every 3 months for up to 1 year from their Final Study Visit regardless of initiation of additional treatments to check for disease progression and survival status. This assessment may be made by telephone interview or performed during the patient's routine clinic visits following completion of participation in the study. If the patient is lost to follow-up public databases can also be searched.

The following list of assessments is based on 14 days of SEL24/MEN1703 treatment in 21-day cycles, further details, including possible exceptions for samples to be collected, are reported in the Schedule of Study Assessments (Table 5) and its footnotes.

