### Follow-Up

- ~ Follow-up assessments (a visit or a telephone call, as per local practice)

**IMPORTANT NOTE:** in addition to the optional time points above described, bone marrow aspirate/biopsy is mandatory at Screening and as soon as the peripheral lab results become consistent with an objective response.

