### **8.3. Completion of the Study**

The study will be completed when all patients have completed their Final Study Visit assessment. On completion of the study, data will be reconciled and the database will be locked for analysis.

Study start is defined by First Patient In (FPI) i.e. when the first patient receives the first dose of study drug. Study Completion is defined by Last Patient Out (LPO) of the study i.e. when the last patient enrolled in the study has completed the last dose of study drug or discontinued for any reason and been followed up to the Final Study Visit.

End of Study is defined as the Final Study Visit of the last subject who discontinues the study treatment.

An addendum (or addenda) to the Clinical Study Report will be generated as required to report any data obtained during the Follow-up Assessments.

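### The SAP gives conflicting censoring dates for overall survival, and the protocol is inconsistent on who is followed for survival

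*SAP*

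**What the plan says.** OS censoring is worded in three places in the SAP:

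- Section 5.4.2: "Patients without the event are censored at the last date of follow-up".
- Section 11.3: for OS, "the censoring date is defined as the date of the last performed visit".
- Section 12.1 splits censored patients in two. "In case of censored information not for drop-out", time runs to the end of the observation period, glossed as study end or end of survival follow-up. For drop-outs it runs to the last date known alive.

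The protocol lets survival status be obtained without a clinic visit. Section 5.1 lists "Follow-up assessments (a visit or a telephone call, as per local practice") and adds: "If the patient is lost to follow-up public databases can also be searched". Contacts are about three months apart for up to one year. The protocol, but not the SAP, also stops them at End of Study. Protocol 8.3 states: "End of Study is defined as the Final Study Visit of the last subject who discontinues the study treatment".

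On who is followed, Protocol 3.6 says "all subjects evaluable for efficacy will be followed for survival/disease status according to local practice". Footnote 18 to Protocol Table 5 instead requires "An assessment of each patient's disease status and AML-related medications administered", with survival status. Protocol 5 and 5.1, SAP 5.1 and footnote 18 of the SAP flow chart carry no efficacy-evaluable restriction.

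**The concern.** Two programmers could each follow the SAP and derive different OS from the same data, because no section takes precedence.

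The 11.3 rule is the more troubling one. If a telephone call is not a visit, a death learned by telephone or from a registry enters at its true date, while a survivor confirmed by the same route is cut back to the last clinic visit. Censoring then depends on outcome: survivors leave the risk set early, deaths stay in, and the Kaplan-Meier curve is too low.

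The 12.1 rule has a milder weakness in the other direction. Neither document schedules a vital-status check at End of Study. A patient censored on that date may not have been confirmed alive since a contact up to three months earlier.

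The follow-up population matters because SAP 12.1 computes OS on both the Safety and Efficacy populations. If sites apply Protocol 3.6 literally, Safety-set patients outside the efficacy-evaluable group have no planned survival follow-up. The protocol does not define that group. The Efficacy population in SAP 7.3 requires a completed first cycle and at least 75% of the drug in it, so it would exclude early stoppers.

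**Working it through.** The documents give no OS assumption, event count or power, so there is no planned figure to reproduce.

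**Worked patient.** OS is date − first dose + 1, with first dose on day 1. Suppose last dose is Cycle 3 Day 14: 2 × 21 + 14 = day 56. The Final Study Visit at its 30-day limit is day 86. Telephone contacts every three months from last dose fall on about days 147, 239, 330 and 421.

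| Case | SAP 11.3 (calls not visits) | SAP 12.1 | Gap |
|---|---|---|---|
| Alive at the 12-month call | day 86 | day 421 (end of survival follow-up) | 335 days |
| Lost after the 6-month call | day 86 | day 239 (last known alive) | 153 days |

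The first gap is 365 − 30 = 335 days. If the year runs from the Final Study Visit, as Protocol 5.1 has it, the gap is 365 days.

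**Effect of the last-visit rule.** This was simulated with 200,000 patients per scenario. The assumptions are not in the documents: exponential survival, median 42 days on drug, each three-monthly contact a clinic visit with probability p, and deaths found at the next contact. The true median is 6.0 months, so true 12-month OS is 0.5^(12/6) = 25%. Early cut-off means 5 months after an 18-month accrual.

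| p (share of contacts in clinic) | 0 | 0.25 | 0.5 | 0.75 | 1 |
|---|---|---|---|---|---|
| Median, full year of follow-up (months) | 5.0 | 5.6 | 5.9 | 6.0 | 6.0 |
| Median, early cut-off (months) | 4.7 | 5.3 | 5.7 | 5.9 | 6.0 |
| 12-month OS, full year (%) | 6.5 | 15.8 | 20.9 | 23.8 | 24.9 |
| 12-month OS, early cut-off (%) | 4.4 | 13.2 | 19.0 | 22.9 | 24.9 |

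**Sensitivity to the assumed survival.** A second simulation used 100,000 patients per scenario, telephone-only contact and last dose on day 14, 35, 56, 77 or 98 with equal probability.

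| True median (months) | Median, 11.3 vs 12.1 (months) | 12-month OS, 11.3 vs 12.1 |
|---|---|---|
| 3 | 2.95 vs 2.99 | 2.2% vs 6.1% |
| 6 | 4.98 vs 5.95 | 6.6% vs 25.0% |
| 9 | 6.13 vs 9.04 | 9.1% vs 39.8% |

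**Other rules, true median 6 months.** With early cut-off, end-of-observation censoring gives 12-month OS of 27.9% if deaths after the last contact stay unknown, and 25.2% if status is confirmed. Last-known-alive censoring gives 24.9% with full follow-up and 25.2% with early cut-off. It falls to 23.1% if a check at cut-off records deaths but not survivors.

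**Protocol 3.6 taken literally.** Early stoppers are assumed to leave drug on days 1–20 and to be censored 30 days later; the rest have a median of 6 months from day 21. With 25% early stoppers:

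| Early stoppers' median OS (months) | 1.5 | 3 | 4.5 | 6 |
|---|---|---|---|---|
| Safety-set median, 3.6 applied (months) | 5.8 | 6.2 | 6.4 | 6.5 |
| Safety-set median, all followed (months) | 4.7 | 5.5 | 6.1 | 6.5 |

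**Scale.** For a cohort of 20, the standard error of a 25% rate is √(0.25 × 0.75 / 20) = 9.7 points.

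**The case against.** The strongest reply is that a visit in 11.3 can be read to include the scheduled follow-up contact. The SAP flow chart appears to place Follow Up among its visit columns, and 5.4.2 speaks of follow-up generally. On that reading most of the bias goes. This stands as a condition on the size. It does not remove the conflict: 12.1 still censors non-drop-outs at the end of observation rather than at a contact, a registry date is not a visit, and the SAP does not say that calls count.

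The headline effects also assume telephone-only contact. With half the contacts in clinic, the median moves by 0.1 month and 12-month OS by about 4 points, less than half the standard error at n = 20. SAP 11.2 commits to quartiles, the median and curves; the 6- and 12-month rates are optional. With a true median of 3 months the median hardly changes. All of this is fair, and it limits the expected damage.

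The end of survival follow-up in 12.1 may mean the patient's own last contact, in which case the upward bias vanishes. Protocol 8.3 also foresees report addenda for follow-up data. The upward bias is therefore only a possibility.

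On Protocol 3.6, the text does not say that others are not followed, the efficacy-evaluable group may not be the SAP's Efficacy population, and the early-stopper share and survival are assumed. The inconsistency remains, but its effect is conditional.

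**Conclusion.** The concern holds. The SAP's OS censoring rules give different dates for the same patient, by 335 days in a case built from the documents' own schedule, and nothing settles which applies.

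If calls are not visits, the 11.3 rule makes censoring depend on outcome and biases OS downward. At an assumed true median of 6 months and a full year of follow-up, the median loss runs from 1.0 month with telephone-only contact to 0.1 month with half the contacts in clinic. The 12-month rate loses 18.5 points (25 − 6.5) and 4.1 points (25 − 20.9) respectively. The loss is larger with longer survival and small for the median with shorter survival. The 12.1 rule can err upward by about 3 points (27.9 against 25), but only if status is unconfirmed at the end of observation.

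Taking Protocol 3.6 literally raises Safety-set OS only if early stoppers survive less well than the rest. Efficacy-set OS is unaffected if the undefined term means that set.

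OS is a descriptive secondary endpoint with no decision rule attached, so this should be fixed but does not threaten the primary objectives.

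**What to change.** State one OS rule, identically, in SAP 5.4.2, 11.3 and 12.1:

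- A patient without a recorded death is censored at the last date known alive from any source (visit, telephone or registry), capped at a stated cut-off date.
- The end-of-observation date is used only when the patient is confirmed alive on it.
- Any vital-status check at cut-off records survivors as alive on that date as well as deaths.
- The last-visit wording is removed for OS.

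Reconcile Protocol 3.6 with footnote 18 and Sections 5 and 5.1 so that all dosed patients are followed for survival.

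The SAP change is wording in three sections and resolves the censoring conflict on its own. The Protocol 3.6 change is one phrase, but it needs an amendment and a few extra telephone contacts for early stoppers. If it is too late for those contacts (the SAP is dated May 2023), the SAP correction should still be made, and the report should say which patients had survival follow-up.
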